5.2.2. Analysis Methods

Descriptive statistics for the actual values and changes from reference will be provided per time point.

Cross-tabulations of the worst toxicity grades through Week 96 versus reference, and cross-tabulations of the worst toxicity grades at Week 96 versus reference will also be provided if applicable. Subject listings of abnormal laboratory values will be provided.

Additionally, the following lipid-related abnormalities according to NCEP categories will be tabulated:

- Triglycerides abnormally high (≥150 mg/dL)
- Total cholesterol abnormally high ($\geq 200 \text{ mg/dL}$)
- LDL abnormally high ($\geq 100 \text{ mg/dL}$)
- HDL abnormally low (< 40 mg/dL)

Hy's Law Criteria

In addition, an analysis will be performed to identify all subjects meeting Hy's law criteria i.e. subjects showing 3-fold or greater elevations above the ULN of ALT or AST and a concomitant elevation of serum total bilirubin to >2xULN, without a concomitant elevated serum ALP (defined as serum alkaline phosphatase activity less than 2× the upper limit of normal).

5.2.3. Creatinine and Glomerular Filtration

5.2.3.1. Serum Creatinine and Cystatin C

Estimated glomerular filtration rate based on the creatinine clearance will be calculated according to the Cockcroft-Gault formula (eGFRcr_{CKD-EPI}) and the CKD-EPI formula (eGFRcr_{CKD-EPI}) and eGFR based on cystatin C clearance will be calculated according to the CKD-EPI formula (eGFRcyst_{CKD-EPI}).

- eGFRcr according to the Cockcroft-Gault formula (unit: mL/min):

Male: $(140 - age in years) \times (weight in kg) = eGFRcr_{CG}(mL/min)$

 $72 \times (\text{serum creatinine in mg/dL})$

Female: $(140 - \text{age in years}) \times (\text{weight in kg}) \times 0.85 = \text{eGFRcr}_{CG} \text{ (mL/min)}$

 $72 \times (\text{serum creatinine in mg/dL})$

- eGFRcr and eGFRcyst according to the CKD-EPI formula (unit: mL/min/1.73m²):

eGFRcr_{CKD-EPI}

Female: $Scr \le 0.7 \text{ mg/dL}$ 144 x $(Scr/0.7)^{-0.329}$ x 0.993^{age}

Scr > 0.7 mg/dL 144 x $(Scr/0.7)^{-1.209}$ x 0.993^{age}

Male: $Scr \le 0.9 \text{ mg/dL}$ 141 x $(Scr/0.9)^{-0.411}$ x 0.993^{age}

Scr >0.9 m	ng/dL 14	1 x (Scr/0.9) ^{-1.209} x 0.993 ^{age}
eGFRcyst _{CKD-EPI}		
Scyst ≤0.8	mg/L 13	3 x (Scyst/0,8) ^{-0.499} x 0.996 ^{age} [x 0.932 if female]
Scyst >0.8	mg/L 13	3 x (Scyst/0,8) ^{-1.328} x 0.996 ^{age} [x 0.932 if female]

Scr = serum creatinine (mg/dL), Scyst = serum cystatin C (mg/L)

The changes from reference in serum creatinine, eGFRcr_{CG} and eGFRcr_{CKD-EPI} and eGFRcyst_{CKD-EPI} at Week 96 will be summarized by treatment arm and using descriptive statistics.

Within-treatment arm comparison versus reference at Week 96 will be assessed using Wilcoxon signed-rank test.

Stages of GFR at reference versus the minimum post-reference GFR value and the last available value will be summarized by count and percent of subjects. Kidney disease stages are defined as follows: 1 (Normal): $GFR \ge 90$; 2 (Mild): GFR 60-89; 3 (Moderate): GFR 30-59; 4 (Severe): GFR 15-29; 5 (Renal Failure): GFR < 15 mL/min).

In addition to the above, the number and proportion of subjects with a >25%, >50% and >75% decrease from reference will be tabulated.

5.2.3.2. Proximal Renal Tubular Function

Proteinuria by Quantitative Assessment

Total urine protein, total urine albumin, urine protein to creatinine ratio (UPCR) and urine albumin to creatinine ratio (UACR) will be summarized by treatment arm and visit using descriptive statistics.

The number and proportion of subjects with UACR and UPCR results in the following categories at Week 96 will be tabulated:

- UACR: $< 30, \ge 30 \text{ to } 300, >300 \text{ mg/g}$
- UPCR: $< 200 \text{ mg/g versus} \ge 200 \text{ mg/g}$

Median (Q1, Q3) percent change from reference over time will be plotted by treatment group.

The evolution over time of total urine protein and total urine albumin will also be presented.

Proteinuria by Urinalysis (Dipstick)

Treatment-emergent proteinuria by urinalysis (dipstick) through Week 96 will be summarized by treatment group. Cross-tabulation of grades at Week 96 versus reference will also be presented.

Other Renal Biomarkers

Selected renal biomarkers retinol binding protein (RBP) and beta-2-microglobulin, RBP to creatinine ratio and beta-2-microglobulin to creatinine ratio will be summarized by treatment arm and visit using descriptive statistics. The proportions of subjects with beta-2-microglobulin to creatinine ratio <=300 mg/g and >300 mg/g will be tabulated.

The number and proportion of subjects with retinal binding protein to creatinine ratio results in the following categories at Week 96 will be tabulated:

• < 50 years of age (at the time of lab assessment): < 130 mcg/g creatinine, \geq 130 mcg/g creatinine

• \geq 50 years of age (at the time of lab assessment): \leq 172 mcg/g creatinine, \geq 172 mcg/g creatinine

Phosphate excretion

Other renal biomarkers include urine fractional excretion of phosphate (FEPO4) that will be summarized by treatment arm and visit using descriptive statistics.

Urine fractional excretion of Phosphate (FEPO4) will be calculated as follows:

• Based on unadjusted serum creatinine:

$$FEPO4 (\%) = (SCr \times UPO4) / (SPO4 \times UCr) \times 100 (\%)$$

The reference, post-reference, and change from reference in FEPO4 will be summarized by treatment arm and visit using descriptive statistics. Median (Q1, Q3) change from baseline in FEPO4 over time will be plotted by treatment group.

Subclinical renal proximal tubulopathy

Potential Markers of Renal Proximal Tubulopathy are:

- 1. Increase in serum creatinine ≥ 0.40 mg/dL from reference.
- 2. Confirmed ≥ 2 grade level increase from reference in graded proteinuria
- 3. Confirmed ≥ 1 grade level increase from reference in graded hypophosphatemia
- 4. Confirmed ≥ 1 grade level increase from reference in graded glycosuria concurrent with serum glucose <=100 mg/dL (normoglycemic glycosuria)

A confirmed laboratory abnormality is defined as an abnormality observed at 2 consecutive postreference measurements or an abnormality observed at 1 measurement followed by study drug discontinuation

A subclinical renal proximal tubulopathy will be defined as confirmed abnormalities in any 2 out of the 4 renal parameters (serum creatinine and one or more of the 3 other markers of tubular dysfunction).

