The primary nonclinical toxicities for TAF are renal and bone toxicity. Based on available data from the ongoing COBI and E/C/F/TDF tablet clinical development programs, decreases in eGFR are anticipated due to the known effects of COBI on the renal tubular excretion of creatinine, without an impact on the renal glomerular function. Studies GS-US-292-0102 and GS-US-236-0118 showed that the E/C/F/TDF tablet, as well as ATV/COBI or DRV/COBI + background regimens were safe and well tolerated in subjects with mild renal impairment (eGFR 50 to 89 mL/min). The combination of D/C/F/TAF is not anticipated to have an effect on actual glomerular filtration rate, monitoring of creatinine along with other standard clinical tests for renal and bone disorders is planned in all clinical studies with the

D/C/F/TAF FDC tablet. The eligibility criteria for study TMC114FD2HTX3001 with the D/C/F/TAF FDC tablet allow the inclusion of subjects with a screening eGFR of ≥70 mL/min. Changes from baseline in serum creatinine, in eGFR based on creatinine clearance (eGFRcreatinine) and in eGFR based on cystatin C clearance (eGFRcystatin C) will be measured in this study. In addition, a renal management algorithm to optimally evaluate and determine the benefit/risk balance for continued participation of subjects whose eGFRcreatinine would decrease <50 mL/min is also included in the study protocol. As recent data suggest that the combined use of COBI and TDF might increase proteinuria (expected to be less with TAF), this study will also assess the effects of the D/C/F/TAF FDC tablet on proteinuria, albuminuria, beta-2-microglobulinuria, and urine retinol-binding protein (RBP).

In addition, assessment of bone mineral density (BMD) is included in the study protocol as a substudy, and follow-up per local medical practice at the discretion of the investigator will be recommended in case a decrease from baseline of >7% in the hip region or >5% in the spine region is demonstrated. Selected bone biomarkers, including C-type collagen sequence (CTX), procollagen type N-terminal propeptide (P1NP), parathyroid hormone (PTH), and 25-hydroxy vitamin D, will be monitored in the substudy.

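### The SAP's beta-2-microglobulin:creatinine cut-off of 300 mg/g lies above its own 200 mg/g boundary for total urine protein, so the split adds nothing to UPCR; the unit is probably wrong

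*SAP*

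**What the plan says.** SAP 5.2.3.2 (Proximal Renal Tubular Function) sets category boundaries for four urinary ratios to creatinine.

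- Under the quantitative proteinuria heading it summarises "urine protein to creatinine ratio (UPCR) and urine albumin to creatinine ratio (UACR"). It counts subjects at Week 96 with UPCR below 200 mg/g against 200 mg/g or more, and with UACR below 30, from 30 to 300, and above 300 mg/g.
- Under other renal biomarkers, the beta-2-microglobulin instruction reads: "beta-2-microglobulin to creatinine ratio <=300 mg/g and >300 mg/g will be tabulated". That sentence names no visit.
- RBP is split by age. The younger group's boundary is "< 50 years of age (at the time of lab assessment): < 130 mcg/g creatinine"; from age 50 the boundary is "172 mcg/g creatinine".

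The units differ between the two tubular markers: mg/g for beta-2-microglobulin, mcg/g for RBP. Neither document gives a source, a derivation or a laboratory reporting unit for the beta-2-microglobulin figure.

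Protocol 1.7 explains why the marker is measured. The study is to "assess the effects of the D/C/F/TAF FDC tablet on proteinuria, albuminuria, beta-2-microglobulinuria, and urine retinol-binding protein (RBP"), because cobicistat combined with TDF may increase proteinuria, and less of this is expected with TAF. Protocol 11.1 lists change in renal biomarkers at Weeks 48 and 96 as a secondary endpoint.

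**The concern.** A threshold for one urinary protein should not exceed the threshold that the same section uses for all urinary protein together. Here it does. The companion tubular marker is also judged on a scale more than a thousand times finer.

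This split is the only categorical beta-2-microglobulin output in the SAP. Programmed as written, it takes its place among the tubular-safety tables but can only pick out subjects whose total proteinuria is already well past the UPCR boundary. If few or no subjects fall above the cut-off, the table could be read as evidence of tubular safety before and after the switch to D/C/F/TAF, when it reflects only where the line was drawn.

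**Working it through.** The 300 mg/g figure is a stated constant with no derivation, so there is nothing to reproduce. The check is whether it is coherent with the other boundaries in its own section.

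**Inputs (all SAP 5.2.3.2)**

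- Beta-2-microglobulin:creatinine cut-off: 300 mg/g
- UPCR boundary: 200 mg/g
- UACR boundaries: 30 and 300 mg/g
- RBP:creatinine boundaries: 130 mcg/g (under 50 years) and 172 mcg/g (50 years and over)

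**Step 1: common units.** With 1 mg = 1,000 mcg:

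- beta-2-microglobulin: 300 mg/g = 300,000 mcg/g
- RBP: 130 mcg/g = 0.130 mg/g and 172 mcg/g = 0.172 mg/g

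**Step 2: against total protein.** 300 / 200 = 1.5. The single-protein cut-off is 50% above the all-protein boundary. It equals the start of the top UACR category.

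**Step 3: part and whole.** Let B be the amount of beta-2-microglobulin, P total urine protein and C urine creatinine. B is part of P, so B/C ≤ P/C, that is, B/C ≤ UPCR. Then:

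- B/C > 300 mg/g implies UPCR > 300 mg/g, hence UPCR ≥ 200 mg/g.
- UPCR ≤ 300 mg/g implies B/C ≤ 300 mg/g, so no such subject can enter the upper category.

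The upper beta-2-microglobulin category is therefore nested inside the upper UPCR category. For a subject to enter it, the share of all urine protein made up of beta-2-microglobulin must exceed 300 / UPCR:

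| UPCR (mg/g) | Share that must be exceeded |
|---|---|
| 300 or less | not possible |
| 500 | 300/500 = 60% |
| 1,000 | 300/1,000 = 30% |
| 3,000 | 300/3,000 = 10% |

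**Step 4: against the companion marker.**

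- 300,000 / 130 = 2,308
- 300,000 / 172 = 1,744

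The factor of 1,000 is the unit step only; the cut-offs themselves differ by 1,744 to 2,308 times.

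**Step 5: the same number in mcg/g (an assumption, not in the documents).** 300 mcg/g = 0.30 mg/g. Then 300/130 = 2.3 and 300/172 = 1.7 times the RBP boundaries, and 0.30/200 = 0.15% of the UPCR boundary. The two tubular markers would be on a similar scale, and the nesting of Step 3 would no longer follow.

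**The case against.** The strongest reply is that little depends on this table. SAP sections 1 and 1.3 confine the document to the Week 96 analysis, with no formal hypothesis. Section 5.2.3.2 also summarises beta-2-microglobulin and its ratio to creatinine by arm and visit as continuous data, alongside the RBP categories, UPCR, UACR, dipstick proteinuria and fractional phosphate excretion. The subclinical tubulopathy definition uses serum creatinine, graded proteinuria, hypophosphatemia and glycosuria, not beta-2-microglobulin. The protocol's between-arm test at Week 48 (section 11.6) is a Wilcoxon rank-sum test on change in the biomarkers and involves no cut-off. All of this stands, and it limits the point to one tabulation.

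Second, nesting within UPCR does not prove that the unit is wrong. RBP and beta-2-microglobulin are different proteins, and nothing in the documents requires their limits to be similar. The figure also coincides with the top UACR boundary, so the documents cannot settle whether the unit alone or the whole entry is at fault. This stands too: mcg/g is an inference.

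Some stronger readings are tempting and should be set aside.

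- A reader might infer that the SAP's tubular outputs cannot detect any abnormality. The outputs listed above do not depend on this cut-off, and even the split could flag a subject with UPCR above 300 mg/g made up largely of beta-2-microglobulin.
- A reader might infer that almost nobody in either arm would exceed 300 mg/g. That needs reference values or a distribution that the documents do not give.
- A reader might infer that the SAP labels UPCR of 200 mg/g or more as abnormal. It only forms two categories there.
- A reader might infer that the randomised TAF–TDF renal comparison is compromised. The Week 48 SAP is not among the documents, so whether it used this cut-off is unknown, and the protocol's own test does not.

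**Conclusion.** The point holds in a limited form. The cut-off is incoherent with its neighbours: 1.5 times the total-protein boundary and 1,744 to 2,308 times the RBP boundaries. As written, the split cannot reveal tubular proteinuria that the UPCR category of 200 mg/g or more does not already capture, so it carries almost no information of its own. A mg-for-mcg slip is the most economical explanation, but remains unconfirmed.

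The conclusion assumes that beta-2-microglobulin counts within measured total urine protein and that both ratios come from the same urine sample with the same creatinine. Protocol 9.1.2.2 and 9.1.3 let a subject who had not fasted return within 72 hours for the biomarker urine, so for some subjects the samples may differ and the inequality would then not be exact. It also compares like visits: the UPCR categories are tabulated at Week 96, while the beta-2-microglobulin sentence gives no visit.

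The consequence is one uninformative, possibly falsely reassuring, secondary safety table. Neither the primary endpoint nor any formal test is affected. Because the protocol names beta-2-microglobulinuria as something the study will assess, the table is worth correcting.

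**What to change.** 1. Ask the central laboratory for the reporting unit of urine beta-2-microglobulin and its reference limit relative to creatinine.
2. Correct the cut-off in SAP 5.2.3.2 and in the table program accordingly. The likely result is a split at 300 mcg/g creatinine (at or below against above), but it should not be adopted until the laboratory confirms both number and unit.
3. State the unit used for categorising, any conversion from the reported unit, and the source of the limit.

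The cost is one unit or value in the SAP and one line of the program. The assays, the collected data and the other renal tables stay as they are.

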5.3. Vital Signs and Physical Examination Findings

5.3.1. Definitions

The following vital signs parameters will be analyzed:

- pulse (bpm)
- systolic blood pressure, SBP (mmHg)
- diastolic blood pressure, DBP (mmHg)
- weight (kg)

Pulse, DBP and SBP are classified in the following abnormality codes:

Abnormality code	Pulse (bpm)	DBP (mmHg)	SBP (mmHg)
Abnormally low	≤ 50	≤ 50	≤ 90
Grade 1 or mild	-	> 90 - < 100	> 140 - < 160
Grade 2 or moderate	-	≥ 100 - < 110	≥ 160 - < 180
Grade 3 or severe	-	≥ 110	≥ 180

Abnormality code	Pulse (bpm)	DBP (mmHg)	SBP (mmHg)
Abnormally high	≥ 120	-	-

In determining abnormalities, the following rules are applied:

- worst grades/abnormalities are determined over the whole observational period for each trial phase separately, including post-reference scheduled *and* unscheduled measurements of that phase.
- The abnormalities 'abnormally low' and 'abnormally high'/grades are considered equally important, i.e. if a subject has as well an abnormally low as an abnormally high or graded value post-reference, both abnormalities are shown in the tables. (This means that the sum of the percentages can be more than 100%).

Definition treatment-emergent:

An abnormality will be considered treatment-emergent in a particular phase if it is worse than the reference corresponding to this phase. If the reference is missing, the abnormality is always considered as treatment-emergent. A shift from 'abnormally low' at reference to 'abnormally high' or 'grade ...' post reference (or vice versa) is also treatment-emergent.

5.3.2. Analysis methods

Descriptive statistics for the actual values and changes from reference per time point will be presented. For weight, comparative treatment phase and single arm treatment phase will be presented for Initial D/C/F/TAF group; data from baseline up to the switch, and from the switch up to Week 96 will be presented for the switch group.

Cross-tabulations for the worst abnormalities versus reference per vital signs test will be produced.

Abnormal physical examination findings will be listed.

5.4. Bone Investigations

5.4.1. Definitions

The following bone formation markers will be analyzed:

- Serum total alkaline phosphatase (ALP)
- Serum type 1 procollagen N-terminal (P1NP)

Bone resorption markers:

Urinary or serum collagen type 1 cross-linked C-telopeptide (CTX)

Other:

- parathyroid hormone (PTH)
- 25-hydroxy vitamin D (25-OH VitD)

DXA scan of spine and hip (data of other regions, e.g. femoral neck may also be analyzed if available):

- BMD values
- BMD T-scores

The BMD status will be derived based on T-scores using the following categories:

_	Osteoporosis	Osteopenia	Normal
T-score	< -2.5	-2.5 to < -1	≥ -1

5.4.2. Analysis methods

Bone Biomarker:

Descriptive statistics for the actual values, change and percent changes from reference per time point will be presented for each bone biomarkers.

DXA scan:

Descriptive statistics for the actual values, change and percent changes from reference per time point will be presented for BMD parameters (including T- and Z-scores). Within-treatment arm comparison versus reference at Week 96 will be assessed using paired t-test.

The proportions of subjects with at least 3% change (decrease and increase separately) from reference in BMD will be presented at Week 96. Percent change from reference will also be tabulated based on thresholds; 5% and 7% (hip only).

BMD status will be tabulated (n, %) separately per time point, based on the T-score categories. Crosstabulations for the BMD status at Week 96 versus reference will be produced.

REFERENCES

- 2. Guidance for Industry. Antiretroviral Drugs Using Plasma HIV RNA Measurements Clinical Considerations for Accelerated and Traditional Approval. October 2002.

ATTACHMENTS

ATTACHMENT 1

PREDEFINED MAJOR PROTOCOL DEVIATIONS-based on the current list

The predefined major protocol deviations of this study are described in the Protocol Deviation Criteria document. The deviations that are considered to have an (possible) impact on efficacy are a subset of the predefined major protocol deviations and are indicated with 'Yes' below (column 'Exclude from Per Protocol Analysis') and if such deviations are reported for a subject, the subject will be excluded from the PP analysis.

In addition to the below table, the following subjects will also be excluded from the per-protocol analysis set:

- Subjects with treatment adherence based on drug accountability derivation ii for the active ARVs (worst D/C/F/TAF adherence between baseline to switch and switch to Week 96 for the Initial D/C/F/TAF treatment group and worst adherence across DRV/COBI FTC/TDF, and D/C/F/TAF for the Late Switch to D/C/F/TAF treatment group) <65%. For the purpose of the per-protocol analysis set only, subjects with missing treatment adherence will be assumed to be above 65%.
- Subjects with no post-baseline viral load measurement (e.g., discontinued within 2 weeks).

29

Sequence No.	Description	Protocol Deviation coded term (DVDECOD)	Exclude from PP	
1	Screening plasma HIV-1 RNA level < 1,000 copies/mL	Entered but did not satisfy criteria	Yes	
2	The subject uses disallowed concomitant therapy specified in the protocol.	Entered but did not satisfy criteria	Yes	
3	The subject has any known allergies to the excipients of the D/C/F/TAF, or DRV/COBI, or TDF/FTC tablets, but the subject was randomized	Entered but did not satisfy criteria	Yes	
4	The dose of Investigational treatment arm (D/C/F/TAF tablet) or the active control arm was temporarily not according to protocol for more than 4 consecutive weeks.	Received wrong treatment or incorrect dose (missed dose or extra dose)	Based on >4 weeks period.	
5	The intake of Investigational treatment arm (D/C/F/TAF tablet) or the active control arm was interrupted for toxicity reasons for more than 4 consecutive weeks.	Received wrong treatment or incorrect dose (missed dose or extra dose)	In that case classified as major and excluded from PP	
6	The intake of Investigational treatment arm (D/C/F/TAF tablet) or the active control arm was interrupted for non - toxicity reasons for more than 4 consecutive weeks, or cumulatively for more than 8 weeks.	Received wrong treatment or incorrect dose (missed dose or extra dose		
7	The subject takes disallowed medication as defined per protocol.	Received a disallowed concomitant treatment	Yes (adjudication based on drug/class and duration).	
8	Subjects not showing genotypic susceptibility to DRV, FTC, TFV	Entered but did not satisfy criteria	Yes	
9	The subject missed two or more consecutive planned visits in the trial	Other	Yes	

Approved, Date: 25 April 2018

Sequence No.	Description	Protocol Deviation coded term (DVDECOD)	Exclude from PP
10	Misallocation of Medkits was observed during Dosage and administration of study drug and subject treated differently than what they were randomized to for more than 4 weeks	Other	Yes
11	After achieving confirmed (consecutive) HIV-1 RNA <50 copies/mL prior to Week 96 and scheduled Week 96 achieving HIV-1 RNA ≥ 50 copies/mL or >1log ₁₀ increase in HIV-1 RNA from the nadir at scheduled Week 96, but no retest in Week 96 window (90-102 weeks)	Other	Yes
12	Subject missed the Week 96 visit.	Other	Yes

31

ATTACHMENT 2

Adverse Events of Interest: List of Preferred Terms

AEOI	AEDECOD (MedDRA v19.1)
Rash AEOI	Acrodynia, Drug Eruption, Generalised erythema, Lupus miliaris disseminatus facei, Mucocutaneous rash, Rash, Rash erythematous, Rash generalised, Rash macular, Rash maculo-papular, Rash maculovesicular, Rash morbilliform, Rash papular, Rash pruritic, Rash rubelliform, Rash scarlatiniform, Red man syndrome, Rash vesicular, Rash follicular, Rash papulosquamous, Dermatitis, Dermatitis acneiform, Dermatitis allergic, Dermatitis herpetiformis, Skin necrosis, Skin reaction
Liver AEOI/Cholestasis and jaundice of hepatic origin	Bilirubin excretion disorder, Cholaemia, Cholestasis, Cholestatic liver injury, Cholestatic pruritus, Drug-induced liver injury, Hepatitis cholestatic, Hyperbilirubinaemia, Icterus index increased, Jaundice, Jaundice cholestatic, Jaundice hepatocellular, Mixed liver injury, Ocular icterus, Parenteral nutrition associated liver disease, Deficiency of bile secretion, Yellow skin

AEOI

AEDECOD (MedDRA v19.1)

Liver AEOI/Hepatic failure, fibrosis and cirrhosis and other liver damage related conditions

Acute hepatic failure, Acute on chronic liver failure, Acute yellow liver atrophy, Ascites, Asterixis, Bacterascites, Biliary cirrhosis, Biliary cirrhosis primary, Biliary fibrosis, Cholestatic liver injury, Chronic hepatic failure, Coma hepatic, Cryptogenic cirrhosis, Diabetic hepatopathy, Drug-induced liver injury, Duodenal varices, Gallbladder varices, Gastric variceal injection, Gastric variceal ligation, Gastric varices, Gastric varices haemorrhage, Hepatectomy, Hepatic atrophy, Hepatic calcification, Hepatic cirrhosis, Hepatic encephalopathy, Hepatic encephalopathy prophylaxis, Hepatic failure, Hepatic fibrosis, Hepatic hydrothorax, Hepatic infiltration eosinophilic, Hepatic lesion, Hepatic necrosis, Hepatic steato-fibrosis, Hepatic steatosis, Hepatitis fulminant, Hepatobiliary disease, Hepatocellular foamy cell syndrome, Hepatocellular injury, Hepatopulmonary syndrome, Hepatorenal failure, Hepatorenal syndrome, Hepatotoxicity, Intestinal varices, Liver and small intestine transplant, Liver and small intestine transplant, Liver dialysis, Liver disorder, Liver injury, Liver operation, Liver transplant, Lupoid hepatic cirrhosis, Minimal hepatic encephalopathy, Mixed liver injury, Nodular regenerative hyperplasia, Non-alcoholic fatty liver, Nonalcoholic steatohepatitis, Non-cirrhotic portal hypertension, Oedema due to hepatic disease, Oesophageal varices haemorrhage, Peripancreatic varices, Portal fibrosis, Portal hypertensive enteropathy, Portal hypertensive gastropathy, Portal vein cavernous transformation, Portal vein dilatation, Portopulmonary hypertension, Renal and liver transplant, Retrograde portal vein flow, Reye's syndrome, Reynold's syndrome, Splenic varices, Splenic varices haemorrhage, Steatohepatitis, Subacute hepatic failure, Varices oesophageal, Varicose veins of abdominal wall, Anorectal varices, Anorectal varices haemorrhage, Intrahepatic portal hepatic venous fistula, Peritoneovenous shunt, Portal shunt, Portal shunt procedure, Small-for-size liver syndrome, Spider naevus, Splenorenal shunt, Splenorenal shunt procedure, Spontaneous intrahepatic portosystemic venous shunt, Stomal varices, Portal tract inflammation

Liver AEOI / Liver-related investigations, signs and symptoms

Alanine aminotransferase abnormal, Alanine aminotransferase increased, Ammonia abnormal, Ammonia increased, Ascites, Aspartate aminotransferase abnormal, Aspartate aminotransferase increased, Bacterascites, Bile output abnormal, Bile output decreased, Biliary ascites, Bilirubin conjugated abnormal, Bilirubin conjugated increased, Bilirubin urine present, Biopsy liver abnormal, Blood bilirubin abnormal, Blood bilirubin increased, Blood bilirubin unconjugated increased, Bromosulphthalein test abnormal, Child-Pugh-Turcotte score abnormal, Child-Pugh-Turcotte score increased, Computerised tomogram liver, Foetor hepaticus, Galactose elimination capacity test abnormal, Galactose elimination capacity test decreased, Gamma-glutamyltransferase abnormal, Gammaglutamyltransferase increased, Guanase increased, Hepaplastin abnormal, Hepaplastin decreased, Hepatic artery flow decreased, Hepatic congestion, Hepatic enzyme abnormal, Hepatic enzyme decreased, Hepatic enzyme increased, Hepatic function abnormal, Hepatic hydrothorax, Hepatic hypertrophy, Hepatic mass, Hepatic pain, Hepatic sequestration, Hepatic vascular resistance increased, Hepatobiliary scan abnormal, Hepatomegaly, Hepatosplenomegaly, Hyperammonaemia, Hyperbilirubinaemia, Hypercholia, Hypertransaminasaemia, Kayser-Fleischer ring, Liver function test abnormal, Liver induration, Liver palpable, Liver scan abnormal, Liver tenderness, Mitochondrial aspartate aminotransferase increased, Molar ratio of total branched-chain amino acid to tyrosine, Oedema due to hepatic disease, Perihepatic discomfort, Retrograde portal vein flow, Total bile acids increased, Transaminases abnormal, Transaminases increased, Ultrasound liver abnormal, Urine bilirubin increased, X-ray hepatobiliary abnormal, 5'nucleotidase increased, Blood alkaline phosphatase abnormal, Blood alkaline phosphatase increased, Blood cholinesterase abnormal, Blood cholinesterase decreased, Deficiency of bile secretion, Glutamate dehydrogenase increased, Haemorrhagic ascites, Hepatic fibrosis marker abnormal, Hepatic fibrosis marker increased, Hypoalbuminaemia, Leucine aminopeptidase increased, Liver function test decreased, Liver function test increased, Liver iron concentration abnormal, Liver iron concentration increased, Model for end stage liver disease score abnormal, Model for end stage liver disease score increased, Periportal oedema, Peritoneal fluid protein abnormal, Peritoneal fluid protein decreased, Peritoneal fluid protein increased, Pneumobilia, Portal vein flow decreased, Portal vein pressure increased, Retinol binding protein decreased, Urobilinogen urine decreased, Urobilinogen urine increased

AEOI

AEDECOD (MedDRA v19.1)

Liver AEOI / Hepatitis, non infectious

Acute graft versus host disease in liver, Allergic hepatitis, Autoimmune hepatitis, Chronic graft versus host disease in liver, Chronic hepatitis, Graft versus host disease in liver, Hepatitis acute, Hepatitis cholestatic, Hepatitis chronic active, Hepatitis chronic persistent, Hepatitis fulminant, Hepatitis toxic, Ischaemic hepatitis, Lupus hepatitis, Non-alcoholic steatohepatitis, Radiation hepatitis, Steatohepatitis, Granulomatous liver disease, Liver sarcoidosis, Portal tract inflammation

Hyperglycaemia AEOI

Acquired lipoatrophic diabetes, Blood 1,5-anhydroglucitol decreased, Blood glucose increased, Diabetes complicating pregnancy, Diabetes mellitus, Diabetes mellitus inadequate control, Diabetes with hyperosmolarity, Diabetic arteritis, Diabetic coma, Diabetic hepatopathy, Diabetic hyperglycaemic coma, Diabetic hyperosmolar coma, Diabetic ketoacidosis, Diabetic ketoacidotic hyperglycaemic coma, Diabetic metabolic decompensation, Fructosamine increased, Fulminant type 1 diabetes mellitus, Gestational diabetes, Glucose tolerance impaired, Glucose tolerance impaired in pregnancy, Glucose urine present, Glycosuria, Glycosuria during pregnancy, Glycosylated haemoglobin increased, Hyperglycaemia, Hyperglycaemic seizure, Hyperglycaemic unconsciousness, Impaired fasting glucose, Insulin resistance, Insulin resistance syndrome, Insulin resistant diabetes, Insulin-requiring type 2 diabetes mellitus, Ketoacidosis, Ketonuria, Ketosis, Latent autoimmune diabetes in adults, Metabolic syndrome, Monogenic diabetes, Neonatal diabetes mellitus, Pancreatogenous diabetes, Type 1 diabetes mellitus, Type 2 diabetes mellitus, Type 3 diabetes mellitus, Urine ketone body present, Hyperosmolar hyperglycaemic state

AEOI

AEDECOD (MedDRA v19.1)

Dyslipidaemia AEOI

Acquired lipoatrophic diabetes, Acquired mixed hyperlipidaemia, Apolipoprotein B/Apolipoprotein A-1 ratio increased, Autoimmune hyperlipidaemia, Blood cholesterol abnormal, Blood cholesterol decreased, Blood cholesterol esterase increased, Blood cholesterol increased, Blood triglycerides abnormal, Blood triglycerides decreased, Blood triglycerides increased, Diabetic dyslipidaemia, Dyslipidaemia, Familial hypertriglyceridaemia, Fat overload syndrome, High density lipoprotein abnormal, High density lipoprotein decreased, High density lipoprotein increased, Hypercholesterolaemia, Hyperlipidaemia, Hypertriglyceridaemia, Hypo HDL cholesterolaemia, Hypotriglyceridaemia, Intermediate density lipoprotein decreased, Intermediate density lipoprotein increased, LDL/HDL ratio decreased, LDL/HDL ratio increased, Lecithin-cholesterol acyltransferase deficiency, Lipid metabolism disorder, Lipids abnormal, Lipids decreased, Lipids increased, Lipoprotein (a) abnormal, Lipoprotein (a) decreased, Lipoprotein (a) increased, Low density lipoprotein abnormal, Low density lipoprotein decreased, Low density lipoprotein increased, Non-high-density lipoprotein cholesterol decreased, Non-high-density lipoprotein cholesterol increased, Primary hypercholesterolaemia, Remnant hyperlipidaemia, Remnant-like lipoprotein particles increased, Total cholesterol/HDL ratio abnormal, Total cholesterol/HDL ratio decreased, Total cholesterol/HDL ratio increased, Type I hyperlipidaemia, Type II hyperlipidaemia, Type IIa hyperlipidaemia, Type IIb hyperlipidaemia, Type III hyperlipidaemia, Type IV hyperlipidaemia, Type V hyperlipidaemia, Very low density lipoprotein abnormal, Very low density lipoprotein decreased, Very low density lipoprotein increased

Lipodystrophy AEOI

Body fat disorder, Facial wasting, Fat redistribution, Fat tissue decreased, HIV lipodystrophy, Lipoatrophy, Lipodystrophy acquired, Lipohypertrophy, Partial lipodystrophy

AEDECOD (MedDRA v19.1)

Immune reconstitution inflammatory AEOI

Immune reconstitution inflammatory syndrome, Mycobacterium avium complex immune restoration disease, Immune Reconstitution Inflammatory Syndrome associated tuberculosis, Immune Reconstitution Inflammatory Syndrome associated Kaposi's sarcoma,

Coronary artery AEOI

Acute coronary syndrome, Acute myocardial infarction, Angina unstable, Blood creatine phosphokinase MB abnormal, Blood creatine phosphokinase MB increased, Coronary artery embolism, Coronary artery occlusion, Coronary artery reocclusion, Coronary artery thrombosis, Coronary bypass thrombosis, Coronary vascular graft occlusion, Kounis syndrome, Myocardial infarction, Myocardial necrosis, Myocardial reperfusion injury, Myocardial stunning, Papillary muscle infarction, Post procedural myocardial infarction, Postinfarction angina, Silent myocardial infarction, Troponin I increased, Troponin increased, Troponin T increased, Blood creatine phosphokinase abnormal, Blood creatine phosphokinase increased, Cardiac ventricular scarring, ECG electrically inactive area, ECG signs of myocardial infarction, Electrocardiogram Q wave abnormal, Electrocardiogram ST segment abnormal, Electrocardiogram ST segment elevation, Electrocardiogram ST-T segment elevation, Infarction, Myocardial necrosis marker increased, Scan myocardial perfusion abnormal, Vascular graft occlusion, Vascular stent occlusion, Vascular stent thrombosis, Angina pectoris, Angina unstable, Anginal equivalent, Arteriosclerosis coronary artery, Arteriospasm coronary, Coronary angioplasty, Coronary arterial stent insertion, Coronary artery bypass, Coronary artery disease, Coronary artery dissection, Coronary artery insufficiency, Coronary artery restenosis, Coronary artery stenosis, Coronary brachytherapy, Coronary bypass stenosis, Coronary endarterectomy, Coronary no-reflow phenomenon, Coronary ostial stenosis, Coronary revascularisation, Coronary vascular graft stenosis, Dissecting coronary artery aneurysm, ECG signs of myocardial ischaemia, External counterpulsation, Haemorrhage coronary artery, Ischaemic cardiomyopathy, Ischaemic mitral regurgitation, Microvascular coronary artery disease, Myocardial ischaemia, Percutaneous coronary intervention, Prinzmetal angina, Stress cardiomyopathy, Subclavian coronary steal syndrome, Subendocardial ischaemia, Arteriogram coronary abnormal, Cardiac stress test abnormal, Computerised tomogram coronary artery abnormal, Computerised tomogram coronary artery abnormal, Electrocardiogram ST segment depression, Electrocardiogram ST-T segment abnormal, Electrocardiogram ST-T segment depression, Electrocardiogram T wave abnormal, Electrocardiogram T wave inversion, Exercise electrocardiogram abnormal, Exercise test abnormal, Post angioplasty restenosis, Stress echocardiogram abnormal, Vascular stent restenosis, Vascular stent stenosis

AEDECOD (MedDRA v19.1)

Severe skin AEOI

Dermatitis bullous, Dermatitis exfoliative, Dermatitis exfoliative generalised, Drug rash with eosinophilia and systemic symptoms, Epidermal necrosis, Erythema multiforme, Exfoliative rash, Oculomucocutaneous syndrome, Skin necrosis, Stevens-Johnson syndrome, Toxic epidermal necrolysis, Toxic skin eruption, Acquired epidermolysis bullosa, Blister, Blister rupture, Bullous impetigo, Conjunctivitis, Corneal exfoliation, Drug eruption, Epidermolysis, Epidermolysis bullosa, Fixed drug eruption, Genital ulceration, HLA-B*1502 assay positive, HLA-B*5801 assay positive, Hypopharyngeal synechiae, Lip exfoliation, Mouth ulceration, Mucocutaneous ulceration, Mucosa vesicle, Mucosal erosion, Mucosal exfoliation, Mucosal necrosis, Mucosal ulceration, Nikolsky's sign, Noninfective conjunctivitis, Oral mucosal blistering, Oral mucosal exfoliation, Oral papule, Oropharyngeal blistering, Pemphigoid, Pemphigus, Penile exfoliation, Skin erosion, Skin exfoliation, Staphylococcal scalded skin syndrome, Stomatitis, Tongue exfoliation, Vaginal exfoliation, Vaginal ulceration, Vulval ulceration, Vulvovaginal rash, Vulvovaginal ulceration

Acute generalised exanthematous pustulosis, Cutaneous vasculitis,

Cardiac conduction AEOI/Conduction defects

Accessory cardiac pathway, Adams-Stokes syndrome, Agonal rhythm, Atrial conduction time prolongation, Atrioventricular block, Atrioventricular block complete, Atrioventricular block first degree, Atrioventricular block second degree, Atrioventricular conduction time shortened, Atrioventricular dissociation, Bifascicular block, Brugada syndrome, Bundle branch block, Bundle branch block bilateral, Bundle branch block left, Bundle branch block right, Conduction disorder, Defect conduction intraventricular, Electrocardiogram delta waves abnormal, Electrocardiogram PQ interval prolonged, Electrocardiogram PR prolongation, Electrocardiogram PR shortened, Electrocardiogram QRS complex prolonged, Electrocardiogram QT prolonged, Electrocardiogram repolarisation abnormality, Lenegre's disease, Long QT syndrome, Paroxysmal atrioventricular block, Sinoatrial block, Trifascicular block, Ventricular dyssynchrony, Wolff-Parkinson-White syndrome

AEDECOD (MedDRA v19.1)

Cardiac conduction AEOI / Torsade de pointes/QT prolongation

Electrocardiogram QT interval abnormal, Electrocardiogram QT prolonged, Long QT syndrome, Long QT syndrome congenital, Torsade de pointes, Ventricular tachycardia

Pancreas AEOI

Amylase abnormal, Hyperlipasaemia, Pancreatic enzymes abnormality, Amylase increased, Lipase abnormal, Pancreatic enzymes abnormal, Blood trypsin increased, Lipase increased, Pancreatic enzymes increased, Hyperamylasaemia, Lipase urine increased, Cullen's sign, Grey Turner's sign, Haemorrhagic necrotic pancreatitis, Hereditary pancreatitis, Ischaemic pancreatitis, Oedematous pancreatitis, Pancreatic abscess, Pancreatic haemorrhage, Pancreatic necrosis, Pancreatic phlegmon, Pancreatic pseudocyst, Pancreatic pseudocyst drainage, Pancreatitis, Pancreatitis acute, Pancreatitis haemorrhagic, Pancreatitis necrotising, Pancreatitis relapsing, Pancreatorenal syndrome

AEDECOD (MedDRA v19.1)

Convulsions AEOI

